16.1.1.4. Subgroup Analyses of PANSS Total Score

For each of the subgroup factors listed in [Section 7.5](#), change from Baseline in PANSS total score at Week 52 will be analyzed using the MMRM method. For the subgroup factors other than country, the MMRM model will include fixed effects for treatment, subgroup, visit, country, Baseline PANSS total

Document: CCI

Author: PPD

Version Number: 0.6

Version Date: 30JAN2023

Template No.: CS_TP_BS016 Revision 6

Reference: CS_WI_BS005

Effective Date: 02Dec2019

score, and treatment-by-subgroup, treatment-by-visit, subgroup-by-visit, and treatment-by-subgroup-by-visit interactions. For the subgroup factor of country, the MMRM model will include fixed effects for treatment, country, visit, Baseline PANSS total score, and treatment-by-country, treatment-by-visit, country-by-visit, and treatment-by-country-by-visit interactions.

Subgroups that do not have at least 2 EFF population subjects with change from Baseline in PANSS total score data available at Week 52/Visit 17 in each of the two treatment groups will be excluded from the analysis.

Estimates obtained from the MMRM model will be presented separately for each subgroup. The nominal p-value for the treatment-by-subgroup interaction at Week 52/Visit 17 will be presented. The presence of a significant interaction effect will be assessed at the 0.10 level for homogeneity of the treatment effect across the different categories of a subgroup factor. In case of a significant interaction effect, estimates by subgroup will be examined to determine the nature of the interaction (qualitative or quantitative). The MMRM results of all subgroup analyses will also be presented using forest plots.

The observed PANSS total score and the change from Baseline values will also be summarized descriptively by treatment group and visit for each subgroup.

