7.2. MULTICENTER STUDIES

This study will be conducted by multiple Investigators at multiple centers in the US and non-US countries, including Russia, Romania, and Ukraine. Randomization is stratified by country.

When specified, statistical analysis will be adjusted for country.

Document: CCI

Author: PPD

Version Number: 0.6

Version Date: 30JAN2023

Template No.: CS_TP_BS016 Revision 6

Reference: CS_WI_BS005

Effective Date: 02Dec2019

A term for treatment-by-country interaction at Week 52/Visit 17 will be explored as part of the subgroup analysis (see [Section 16.1.1.4](#)). A significant interaction effect is defined as having a nominal p- value ≤ 0.10 . Additionally, graphical methods (i.e. Forest plots) will be used to present the analysis results separately for each country and to assess whether the interaction, if there is one, is quantitative (i.e. the treatment effect is consistent in direction but not in size) or qualitative (i.e. the treatment is beneficial for some but not for other countries).

Center pooling will not be implemented in the analyses for this study.

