7.5. EXAMINATION OF SUBGROUPS

Subgroup analysis will be conducted for subjects as stated in [Section 16.1.1.4](#) for PANSS, [Section 16.2.1](#) for CGI-S and [Section 17.1.10](#) for Adverse Events.

Document: CCI

Author: PPD

Version Number: 0.6

Version Date: 30JAN2023

Template No.: CS_TP_BS016 Revision 6

Reference: CS_WI_BS005

Effective Date: 02Dec2019

The following subgroups will be assessed:

- Geographic region:
 - US
 - Non-US
- Country:
 - United States
 - Russia
 - Romania
 - Ukraine
- Sex:
 - Female
 - Male
- Age group:
 - ≤ 40 years
 - > 40 years
- Race (in 3 categories):
 - White (White)
 - Black (Black or African American)
 - Other (All other races combined)
- Number of prior hospitalizations for treatment of schizophrenia:
 - 0
 - 1

Document: CCI

Author: PPD

Version Number: 0.6

Version Date: 30JAN2023

Template No.: CS_TP_BS016 Revision 6

Reference: CS_WI_BS005

Effective Date: 02Dec2019

- 2
- 3
- 4 or more
- Duration of schizophrenia (years):
 - <5
 - ≥ 5
- BMI (kg/m^2) categories:
 - Underweight: $<18.5 \text{ kg}/\text{m}^2$
 - Normal: ≥ 18.5 to $<25.0 \text{ kg}/\text{m}^2$
 - Overweight: ≥ 25.0 to $<30.0 \text{ kg}/\text{m}^2$
 - Obese: $\geq 30.0 \text{ kg}/\text{m}^2$
- Baseline patient type based on UPSM factor scores at Baseline (only used in the subgroup analysis of PANSS total score) (Hopkins et al. 2020):
 - Type 1: Prominently Disorganized
 - Type 2: Prominently Negative
 - Type 3: Prominently Hostile
 - Type 4: Prominently Positive
 - Type 5: Prominently Affective

Subjects will be classified into one of 5 patient types based on their PANSS UPSM factor scores at Baseline. See [APPENDIX 12](#) for details of how the classification will be made.

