16.1.1. OBSERVED VALUES AND CHANGE FROM BASELINE IN PANSS TOTAL SCORE

16.1.1.1. Exploratory Analysis of PANSS Total Score

Data will be analyzed using a mixed model for repeated measures (MMRM) under the MAR assumption. Under this assumption, the efficacy outcome of subjects in each treatment group after early discontinuation will exhibit the same future evolution as subjects in the same group remaining in the study. The MMRM model will include fixed factors for treatment, visit (Weeks 1, 4, 8, 16, 24, 32, 40, 48, 52; as a categorical variable), country, and treatment-by-visit interaction and include Baseline PANSS total score as a covariate. An unstructured covariance matrix will be used to model the within-subject correlation. Kenward-Roger approximation will be used to calculate the denominator degrees of freedom.

The least squares (LS) mean difference in PANSS total score change from Baseline at Week 52 (SEP-363856 group vs. Quetiapine), their standard errors, the two-sided 95% CIs, and the associated nominal p-values will be calculated from the MMRM model.

In addition, the following statistics will be reported in the MMRM table:

Document: CCI

Author: PPD

Version Number: 0.6

Version Date: 30JAN2023

Template No.: CS_TP_BS016 Revision 6

Reference: CS_WI_BS005

Effective Date: 02Dec2019

- The LS mean difference in PANSS total score change from Baseline at Weeks 1, 4, 8, 16, 24, 32, 40, 48; their standard errors; the two-sided 95% CIs; and the associated nominal p-values.
- The LS mean of PANSS total score change from Baseline at each time point for each treatment group, their standard errors, and the two-sided 95% CIs.
- Within group effect size at each time point, calculated as the LS mean of each treatment group at each time point divided by the model estimate of standard deviation, obtained as the square root of the corresponding diagonal element of the residual covariance matrix (R matrix from PROC MIXED).
- Between group effect size vs. Quetiapine at each time point, calculated as the LS mean difference of each SEP-363856 group vs. Quetiapine at each time point divided by the model estimate of standard deviation, obtained as the square root of the corresponding diagonal element of the residual covariance matrix (R matrix from PROC MIXED).

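### The region subgroup MMRM contains both region and country, so per-arm LS means by region are non-estimable under standard weights; treatment differences and the interaction test are unaffected

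*SAP*

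**What the plan says.** Section 16.1.1.4 of the SAP gives two subgroup models for change from Baseline in PANSS total score at Week 52.

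- **All factors except country:** "For the subgroup factors other than country, the MMRM model will include fixed effects for treatment, subgroup, visit, country", then Baseline PANSS total "score, and treatment-by-subgroup, treatment-by-visit, subgroup-by-visit, and treatment-by-subgroup-by-visit interactions".
- **Country:** "For the subgroup factor of country, the MMRM model will include fixed effects for treatment, country, visit, Baseline PANSS total score", with the corresponding country interactions and no second geographic term.

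Section 7.5 lists "Geographic region", with levels US and Non-US, as a subgroup factor, so it falls under the first model. Section 7.2 places the study "at multiple centers in the US and non-US countries, including Russia, Romania, and Ukraine", and Sections 7.1 and 7.5 list the same four countries. The US region is therefore the United States, and the Non-US region is the other three countries.

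On output, Section 16.1.1.4 says: "Estimates obtained from the MMRM model will be presented separately for each subgroup". It also calls for the Week 52 interaction p-value and forest plots. Section 16.1.1.1 lists what the main MMRM table reports, including per-arm LS means with standard errors, confidence intervals and within-group effect sizes. Section 16.2.1 applies Section 16.1.1.4 to CGI-S.

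The readable text neither nests country within region nor states how countries are weighted in the LS means.

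**The concern.** A factor and a coarser grouping of that factor should not both enter a model as separate main effects if LS means are wanted for the grouping. The SAP recognises this for country, which gets its own model, but makes no such provision for region. The data cannot say how much of the US versus Non-US contrast belongs to the region effect and how much to the country effects. A standard LS mean by region depends on that split.

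At stake are the model-adjusted values per arm within each region, for two scales. These values show which arm drives a regional difference in treatment effect. The possible remedies do not all fit the same model, so the SAP should name one.

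**Working it through.** The documents give no figure to reproduce here. The check concerns rank and estimability.

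**Inputs.** 2 arms; 2 regions and 4 countries (Sections 7.1, 7.2, 7.5); 9 categorical visits, "visit (Weeks 1, 4, 8, 16, 24, 32, 40, 48, 52; as a categorical variable" (Section 16.1.1.1); a baseline covariate; the interactions in Section 16.1.1.4. Every arm-by-country cell was filled with an arbitrary 12 subjects. The number does not matter for estimability as long as the cells are filled.

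**Columns, one per class level:**

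1 intercept + 2 treatment + 2 region + 9 visit + 4 country + 1 baseline + 4 (treatment × region) + 18 (treatment × visit) + 18 (region × visit) + 36 (treatment × region × visit) = 95.

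**Rank.** The computed rank is 39, which equals 2 × 2 × 9 = 36 cell means + 1 baseline + 2 for country. Country nominally carries 4 − 1 = 3 degrees of freedom and adds only 2. One is aliased with region.

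A rank below 95 is not itself a fault, since any model coded this way is over-parameterised. What matters is whether the linear functions of interest are estimable.

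**Criterion.** A linear function L is estimable if and only if L = L(X⁻X).

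**Week 52 results:**

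| Country weights | Four arm-by-region LS means | Within-region treatment differences | Interaction |
|---|---|---|---|
| Equal, 1/4 each (standard) | none estimable | estimable | estimable |
| Overall unequal weights (0.5, 0.2, 0.1, 0.2) | none estimable | estimable | estimable |
| Confined to region (US: 1; Non-US: 1/3 each) | all estimable | estimable | estimable |

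**Why.** The US-region indicator and the United States indicator are the same column. Add δ to the region-US effect and subtract δ from the country-US effect, and no fitted value changes. If w is the weight on the United States, the US LS mean moves by δ(1 − w) and the Non-US LS mean by −δw. Neither moves only if w = 1 for the US mean and w = 0 for the Non-US mean. No single weight applied to both regions can satisfy that.

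With δ = 10 and w = 1/4:

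- change in fitted values: 0
- US LS mean: 10 × (1 − 0.25) = +7.5
- Non-US LS mean: −10 × 0.25 = −2.5
- treatment difference within a region: 7.5 − 7.5 = 0

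Region and country terms enter both arms identically, so they cancel from the within-region differences and from the interaction.

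**Control.** A subgroup crossed with country (sex) put through the same model gives four estimable LS means. The cause is that region is determined by country.

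**Remedies.** Nesting country within region, or confining weights to each region, spans the same column space (rank 39) and makes all four LS means estimable. Dropping country (rank 39 − 2 = 37) also makes all four estimable.

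**The case against.** The strongest reply is that Section 16.1.1.4 is about homogeneity of the treatment effect, and everything it names for that purpose survives: within-region differences, the interaction p-value and forest plots of differences. That stands.

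Second, Section 16.1.1.4 refers only to estimates from the MMRM and does not itself name per-arm LS means. They are inferred from the list in Section 16.1.1.1. That also stands, so the loss applies if the region table follows that list.

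Third, the weighting may be set out of sight. Appendix 3, which Section 16.1.1.3 cites for sample SAS code, is redacted, and the output templates are not in the public documents. If either sets within-region weights for this model, the point is already met. The model stated in the text does not change, and a clause there would remove the doubt.

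Fourth, much of the information appears elsewhere. The separate country model gives per-arm United States estimates and one set per non-US country, and Section 16.1.1.4 adds descriptive summaries by subgroup. The main gap is a pooled, model-adjusted Non-US mean per arm.

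A reader might also infer that the remedy would be chosen after unblinding to suit the results. The documents do not support this. The defect depends on the region and country coding, not on outcomes or treatment codes, so a dry run on blinded data would expose it. Nor do they rank region as the leading subgroup: Section 7.5 lists it among several.

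**Conclusion.** The model as written does not deliver per-arm LS means by region under standard weights. All four at Week 52 are non-estimable for PANSS total score, together with their standard errors, confidence intervals and within-group effect sizes if these are presented. The same holds for CGI-S. Between-arm results by region, including between-group effect sizes built on the differences, are unaffected.

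The conclusion assumes that the four countries map to the two regions as listed, that all arm-by-country cells are filled, and that no within-region weighting is set in redacted material.

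Two stronger readings should be resisted. One is that the region subgroup analysis as a whole fails; it does not, because the differences and the interaction are estimable under every weighting tried. The other is that the trial's main conclusions are exposed. The primary endpoint is adverse event incidence, Protocol Section 15.3.5 calls all efficacy analyses exploratory, and the adverse event odds-ratio model in SAP Section 17.1.11 uses region without country.

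Severity is minor: a specification error worth correcting.

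**What to change.** Add one clause to SAP Section 16.1.1.4: for the geographic region factor only, country enters nested within region, country(region). Alternatively, state that LS means by region use country weights confined to that region, and give those weights. Section 16.2.1 then carries the change to CGI-S without further edits.

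The cost is one sentence and the matching program line. Fitted values, treatment differences and the interaction test do not change.

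Dropping country from the region model is the second choice. It makes the LS means estimable, but it removes adjustment among Russia, Romania and Ukraine although randomization is stratified by country (SAP Section 3.2), and it can alter treatment differences that are estimable now.

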16.1.1.5. Other Analyses of PANSS Total Score

LS Means (+/- Standard Error) of PANSS total score change from Baseline over time based on MMRM estimates will be plotted as described in the figure shell.

The observed values of PANSS total score at Baseline and each scheduled post-Baseline visit will be summarized descriptively. The Baseline PANSS total score will be derived as described in [Section 6.2](#).

The change from Baseline in PANSS total score will be summarized for each scheduled post-Baseline visit. The change from Baseline in PANSS total score will be derived as described in [Section 6.7](#).

PANNS total score will also be summarized by subgroups as listed in [Section 7.5](#).

16.1.2. OBSERVED VALUES AND CHANGE FROM BASELINE IN PANSS SUBSCALE SCORES

For PANSS subscale scores, the change from baseline at each scheduled post-Baseline will be analyzed as described in [Sections 16.1.1.1](#) and [16.1.1.3](#) (Analysis of covariance (including LOCF)).

Document: CCI

Author: PPD

Version Number: 0.6

Version Date: 30JAN2023

Template No.: CS_TP_BS016 Revision 6

Reference: CS_WI_BS005

Effective Date: 02Dec2019

The observed values of PANSS subscale scores at Baseline and each scheduled post-Baseline visit will be summarized descriptively. The Baseline PANSS subscale scores will be derived as described in [Section 6.2](#).

The change from Baseline in PANSS subscale scores will be summarized for each scheduled post-Baseline visit. The change from Baseline in PANSS subscale scores will be derived as described in [Section 6.7](#).

16.1.3. OBSERVED VALUES AND CHANGE FROM BASELINE IN PANSS MARDER FACTOR SCORES

For PANSS Marder factor scores, the change from baseline at each scheduled post-Baseline will be analyzed as described in [Sections 16.1.1.1](#) and [16.1.1.3](#) (Analysis of covariance (including LOCF)).

The observed values of PANSS Marder factor scores at Baseline and each scheduled post-Baseline visit will be summarized descriptively. The Baseline PANSS Marder factor scores will be derived as described in [Section 6.2](#).

The change from Baseline in PANSS Marder factor scores will be summarized for each scheduled post-Baseline visit. The change from Baseline in PANSS Marder factor scores will be derived as described in [Section 6.7](#).

16.1.4. OBSERVED VALUES AND CHANGE FROM BASELINE IN PANSS UPSM FACTOR SCORES

For PANSS UPSM factor scores, the change from baseline at each scheduled post-Baseline will be analyzed as described in [Sections 16.1.1.1](#) and [16.1.1.3](#) (Analysis of covariance (including LOCF)).

The observed values of PANSS UPSM factor scores at Baseline and each scheduled post-Baseline visit will be summarized descriptively. The Baseline PANSS UPSM factor scores will be derived as described in [Section 6.2](#).

The change from Baseline in PANSS UPSM factor scores will be summarized for each scheduled post-Baseline visit. The change from Baseline in PANSS UPSM factor scores will be derived as described in [Section 6.7](#).

Document:

CCI

Author:

PPD

Version Number:

0.6

Version Date:

30JAN2023

Template No.: CS_TP_BS016 Revision 6

Reference: CS_WI_BS005

Effective Date: 02Dec2019

16.1.5. OBSERVED VALUES AND CHANGE FROM BASELINE IN PANSS UPSM TOTAL FACTOR SCORE

For PANSS UPSM total factor scores, the change from baseline at each scheduled post-Baseline will be analyzed as described in [Sections 16.1.1.1](#) and [16.1.1.3](#) (Analysis of covariance (including LOCF)).

The observed values of PANSS UPSM total factor score at Baseline and each scheduled post-Baseline visit will be summarized descriptively. The Baseline PANSS UPSM total factor score will be derived as described in [Section 6.2](#).

The change from Baseline in PANSS UPSM total factor score will be summarized for each scheduled post-Baseline visit. The change from Baseline in PANSS UPSM total factor score will be derived as described in [Section 6.7](#).

16.1.6. PROPORTION OF SUBJECTS WHO ACHIEVE A RESPONSE

PANSS response is defined as a 20% or greater improvement (i.e. decrease) in PANSS total score from Baseline.

The percent change in PANSS total score from Baseline will be calculated by:

$$\frac{\text{PANSS total score at a visit or the Week 52 LOCF endpoint} - \text{PANSS total score at Baseline}}{\text{PANSS total score at Baseline} - 30} \times 100\%$$

For each subject, the responder indicator will be set to Y if the percent change is negative and the magnitude is equal to or greater than 20%. The indicator will be set to N if the percentage is negative but the magnitude is less than 20% or the percentage is non-negative. The indicator will be set to missing if the percentage is missing.

In addition, PANSS response defined by two more stringent thresholds will be assessed; that is, having a 30% or greater and 50% or greater improvement in PANSS total score from Baseline.

PANSS response at all three thresholds will be derived for all post-Baseline time points.

PANSS response at each scheduled visit and at the LOCF endpoint will be analyzed using a logistic regression model with responder indicator as the dependent variable and include factors for treatment and geographic region, and include Baseline PANSS total score as a covariate. The Number Needed to Treat (NNT) will be provided:

- The NNT for each SEP-363856 group will be derived as:

Document: CCI

Author: PPD

Version Number: 0.6

Version Date: 30JAN2023

Template No.: CS_TP_BS016 Revision 6

Reference: CS_WI_BS005

Effective Date: 02Dec2019

- $$\text{NNT} = \frac{1}{\text{Risk Reduction (RR)}} = \frac{1}{\text{PANSS Response Rate}_{\text{SEP-363856}} - \text{PANSS Response Rate}_{\text{Quetiapine XR}}}$$
- Only positive NNT results will be presented. The NNT results will be provided in whole numbers with any fractional values rounded up to the nearest whole number. The 95% CI of NNT will also be presented and are computed by taking the reciprocal of the 95% CI lower and upper bounds of the RR when both bounds are positive. The lower confidence limit will be rounded down to the largest whole number that is less than the computed estimate, and the upper confidence limit will be rounded up to the smallest whole number that is greater than the computed estimate.

The number and percentage of subjects who achieve a PANSS response will also be summarized descriptively by treatment group and visit.

Lastly, the proportion of subjects achieving a given percentage change threshold in PANSS total score from Baseline at the LOCF endpoint will be calculated for each treatment group. This calculation will be performed at multiple thresholds, starting from -100% and increases at 5% increments or until all subjects are accounted for in all treatment groups, with 5% increments.

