3.4. DETERMINATION OF SAMPLE SIZE

A total of 300 subjects are expected to be enrolled from approximately 50 global sites, including the US and Europe. Subjects will be assigned randomly to receive SEP-363856 or active comparator in an allocation ratio of 2:1. The determination of sample size was based upon clinical considerations. The sample size of 300 subjects will provide approximately 80 subjects who are expected to complete 1 year

Document: CCI

Author: PPD

Version Number: 0.6

Version Date: 30JAN2023

Template No.: CS_TP_BS016 Revision 6

Reference: CS_WI_BS005

Effective Date: 02Dec2019

of treatment with SEP-363856 to support sufficient long-term safety data on SEP-363856.

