6.6. STATISTICAL TESTS

The default significance level will be 5%; confidence intervals (CIs) will be 95%; and all p-values will be two-sided, unless otherwise specified in the description of the analyses or the outputs.

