7.4. MULTIPLE COMPARISONS/ MULTIPLICITY

No multiplicity adjustment is defined for analysis. Nominal p-values (i.e. without multiplicity adjustment) will be reported for statistical tests.

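### The NNT for PANSS response appears only when SEP-363856 has the higher observed rate, and its confidence interval is undefined unless both limits are positive

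*SAP*

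**What the plan says.** SAP section 16.1.6 analyses PANSS response at each scheduled visit and at the LOCF endpoint, for improvements of at least 20%, 30% and 50%. It adds an NNT: "The NNT for each SEP-363856 group will be derived as" one divided by the SEP-363856 response rate minus the quetiapine XR response rate, a quantity that the SAP labels RR, for risk reduction. Two display rules follow. The first is "Only positive NNT results will be presented". The second concerns the 95% CI of the NNT, which is to be presented and is "computed by taking the reciprocal of the 95% CI lower and upper bounds of the RR when both bounds are positive". Nothing is said about a CI that includes zero or lies wholly below zero.

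The same section also provides a logistic regression of response with a treatment factor, the number and percentage of responders by arm and visit, and the proportion of each arm reaching successive percentage-change thresholds at LOCF. None of these is restricted by direction.

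The general conventions are two-directional. Section 6.6 reads "The default significance level will be 5%; confidence intervals (CIs) will be 95%; and all p-values will be two-sided", and section 7.4 reads "No multiplicity adjustment is defined for analysis".

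**The concern.** The comparator is active, and nothing in either document presumes that SEP-363856 will have the higher response rate, so a negative difference is an ordinary outcome. A statistic that is printed when the difference is positive and left blank when it is negative is selected on its own sign. Anyone who collects the NNTs from the tables will find only values favouring SEP-363856, whatever the truth.

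The gap in the CI rule adds to this. An NNT based on a small, inconclusive positive difference would be printed, and the plan does not say what interval, if any, goes with it. The selection operates in many cells: three thresholds at nine post-Baseline PANSS visits plus LOCF gives 3 × (9 + 1) = 30 possible NNTs, all without multiplicity adjustment.

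At stake is the absolute-scale comparison of response. As far as the text shows, the NNT is the only between-arm measure on that scale. The CI of the rate difference is mentioned only as a step towards the CI of the NNT.

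**Working it through.** The documents give no NNT, response rate or power for this endpoint, so there is no planned figure to reproduce. The check has two parts.

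**1. Sign logic (no assumptions needed).** Write d = p(SEP-363856) − p(quetiapine XR) for the observed rates, and NNT = 1/d.

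- NNT > 0 if and only if d > 0. So an NNT is shown only when SEP-363856 has the higher observed rate.
- Both CI limits are positive if and only if the lower limit of d is above zero. That is the only case with a stated method.
- There is no stated method for lower limit ≤ 0 ≤ upper limit, or for upper limit < 0.

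**2. Illustration.** Inputs from SAP section 3.4: "A total of 300 subjects are expected to be enrolled from approximately 50 global sites", "in an allocation ratio of 2:1", which gives 300 × 2/3 = 200 and 300 × 1/3 = 100. The same section also says: "The sample size of 300 subjects will provide approximately 80 subjects who are expected to complete 1 year" on SEP-363856.

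Assumptions, not in the documents:

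- Quetiapine XR has the same retention as SEP-363856: 80/200 = 40%, so 40 of 100 complete.
- Early visits and LOCF have about 95% of each arm: 190 and 95.
- Response rates are 30% to 50%.
- The CI is an unpooled Wald 95% interval, d ± 1.96 × √[p1(1−p1)/n1 + p2(1−p2)/n2]. The SAP does not name the interval.

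Worked examples at 200 versus 100:

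| Observed rates, SEP-363856 vs quetiapine XR | d (95% CI), points | 1/d | What the SAP rule yields |
|---|---|---|---|
| 55% vs 40% | +15.0 (+3.2 to +26.8) | 6.67 | NNT 7, CI 3 to 32 |
| 40% vs 55% | −15.0 (−26.9 to −3.1) | −6.67 | nothing |
| 50% vs 40% | +10.0 (−1.8 to +21.8) | 10 | NNT 10; CI undefined |
| 40% vs 50% | −10.0 (−21.9 to +1.9) | −10 | nothing |

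First row: the standard error is √(0.55×0.45/200 + 0.40×0.60/100) = √0.0036375 = 0.0603, so the half-width is 0.118 and the limits are 0.0318 and 0.2682. Their reciprocals are 31.5 and 3.7, rounded outward as the SAP directs. The second row is the mirror image and equally conclusive, but produces no output. In the third row the reciprocals of the limits are −54.3 and 4.6, which do not bound a single interval.

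Probability that an NNT (necessarily favouring SEP-363856) is shown in one cell, by exact summation over two binomials:

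| True rates, SEP-363856 vs quetiapine XR | 190 vs 95 | 80 vs 40 |
|---|---|---|
| 40% vs 40% | 48% | 48% |
| 35% vs 40% | 19% | 28% |
| 30% vs 40% | 4% | 13% |

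At 40% in both arms with 190 versus 95, the CI of d lies wholly above zero in 2.8% of cells, wholly below in 2.4%, and spans zero in 94.8%. So about 1 − 2.8/48.4 = 94% of the NNTs shown would have no defined interval.

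**The case against.** The strongest reply is that nothing is concealed. Responder counts and percentages by arm, the logistic regression and the LOCF threshold table are all reported in either direction. A reader can subtract two percentages, and knowing the rule, can read a blank NNT as SEP-363856 not being higher. The rule was fixed in the SAP ahead of unblinding, so it is not selection after the fact. Protocol section 15.3.5 calls all efficacy analyses exploratory, the primary endpoint is adverse-event incidence, and no decision rule uses the NNT. All of this stands, and it limits the weight of the point. It does not supply a reason to filter a statistic by its sign.

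A reader might infer that the SAP suppresses the CI unless the result is significantly positive. The text does not say so. It gives a method for one case and is silent on the rest, so the accurate criticism is that the rule is incomplete.

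A reader might also take the low rate of available CIs under no difference, about 3%, as evidence of one-way reporting. Mostly it is not: about 95% of intervals span zero, and the reciprocal then fails in the same way whichever arm is ahead. The directional part is the 2.4% of intervals lying wholly below zero.

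Finally, SAP section 8 refers to output templates that are not available here. A shell might already print the rate difference with its CI.

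**Conclusion.** The point holds as a minor reporting bias confined to the NNT output. By its own definition and display rule, that output can only show results favouring SEP-363856, and its interval is undefined whenever the CI of the difference is not wholly positive. The direction of the bias follows from the text alone.

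The size is illustrative. It rests on assumed response rates, on assumed arm sizes of 190 versus 95 or 80 versus 40, and on treating each cell separately. On those terms a favourable NNT is shown in about 48% of cells when the arms are truly equal, and in 19% to 28% when SEP-363856 is truly 5 points worse.

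The documents do not support the stronger inference that unfavourable response results are withheld from the report, since other prespecified outputs show them in either direction. No primary or safety conclusion is touched.

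**What to change.** In SAP section 16.1.6, delete the sentence restricting presentation to positive NNTs. For every threshold and time point:

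- Report the response-rate difference, SEP-363856 minus quetiapine XR, with its 95% CI, and name the interval method.
- Label the reciprocal as NNT when the difference is positive and as NNH when it is negative. Leave it blank only when the difference is exactly zero.
- Give the reciprocal CI when both limits have the same sign, in either direction. When the CI spans zero, leave it on the difference scale and say so in a footnote.

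The cost is one SAP paragraph and the corresponding table change, with no new data. The consequence for the sponsor is that some unfavourable values will be shown.
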